**NOTES :**

- T = Table, F = Figure, L = Listing, Y = Yes display generated.
- Stats Analysis = Represents TF related to any formal statistical analyses (i.e. modeling) conducted.
- Summary = Represents TF related to summaries (i.e. descriptive statistics) of the baseline, post-treatment and change from baseline for the primary efficacy analyses method.
- Individual = Represents L related to any displays of individual subject observed raw data.

**12.3.2 Analysis Method of the Efficacy Endpoints (rTNSS, iTNSS, RQLQ(S)):  
Mixed Model Repeated Measures Approach**

**12.3.2.1 Change from baseline in the average AM rTNSS over the first 6, 30 and 52 weeks of treatment**

The efficacy endpoints rTNSS will be analyzed using a mixed model repeated measures model, adjusting for covariates that include treatment, site, baseline and week as the within-subject effect (for both the FAS and the PPS). The interactions of

## STATISTICAL ANALYSIS PLAN

|  |                                    |                                  |
|--|------------------------------------|----------------------------------|
| Protocol Number:
GPL/CT/2014/018/III
(Study No. GSP 301-303) | SAP Version Number:
Version 1.0 | SAP Version Date:
04-Apr-2017 |
|--|------------------------------------|----------------------------------|

site-by-treatment and baseline-by-treatment will be investigated separately in the model and will only be included in final model if they are statistically significant at the  $\alpha=5\%$  level. An unstructured (UN) covariance will be assumed. If the model does not converge using the unstructured covariance structure, the autoregressive (order 1) AR(1) structure will be used. If this also does not converge other covariance structures deemed appropriate to fit the data will be used. This method will assume that any missing data is Missing at Random (MAR). The statements of a SAS PROC MIXED analysis would be (if the interactions of treatment\*baseline and treatment\*site is not statistically significant):

```
proc mixed;  
class subject treatment site week;  
model change = treatment site baseline week;  
repeated week / subject = subject type=UN;  
lsmeans treatment / cl diff e ;  
ods output lsmeans=lsmeans ;  
ods output diffs=diffs ;  
run ; quit ;
```

The adjusted means for each treatment and the estimated treatment differences for the treatment comparisons will be presented together with 95% confidence intervals for the differences and p-values for the treatment comparisons. The adjusted means and estimated treatment differences for the treatment comparisons will also be plotted, with corresponding 95% confidence intervals.

The responses for the first 6, 30 and 52 weeks of treatment will all be analysed in separate statistical models.

A multiple, imputation-based approach may be considered for handling missing data for AM rTNSS upon review of amount of missing data observed.

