## 1.0 Changes to the Protocol Defined Statistical Analysis Plan

- The protocol states that the efficacy analysis will be conducted using an analysis of covariance (ANCOVA) model (adjusting for study treatment group, site and baseline). The efficacy analysis will now be analyzed using a mixed models repeated measures (MMRM) model. This will be more applicable to the design of the study, and assesses missing data using the Missing at Random (MAR) assumption. More detail is in Section [12.3](#).
- The protocol states that ‘A multiple, imputation-based approach where complete data sets are drawn will be used for handling missing data in the efficacy analysis.’ Because assessing efficacy is a secondary objective of the study, the sentence has been modified to state ‘A multiple, imputation-based approach *may* be considered for handling missing data for AM reflective Total Nasal Symptom Score (rTNSS) and AM instantaneous Total Nasal Symptom Score (iTNSS) upon review of amount of missing data observed’. More details in Section [12.3](#).
- The protocol states that the computer-generated randomization scheme will be reviewed and approved by an independent statistician and the randomization will be stratified by site. This was inaccurately stated. The computer-generated randomization scheme will be reviewed and approved by a statistician and the randomization will not be stratified by site. More detail is in Section [7.0](#).
- The protocol has defined the Full Analysis Set (FAS) as ‘The FAS will consist of all subjects who are randomized and received at least 1 dose of Investigational Product (IP) and have at least 1 post-baseline efficacy assessment.’ To add more clarity the definition of the FAS is ‘The FAS will consist of all subjects who are randomized and received at least 1 dose of IP and have at least 1 post-baseline AM rTNSS assessment.’

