**12.3.2.3 Change from baseline in the overall RQLQ(S) score at Weeks 6, 30, and 52**

RQLQ(S) (for the FAS) will be analyzed using similar methods as described in Section [12.3.2.1](#), with the following differences:

- Interaction of week-by-treatment will be included in the statistical model
  - Addition of week\*treatment interaction in SAS model statement
  - Week\*treatment interaction stated in SAS lsmeans statement
- The responses at 6, 30 and 52 weeks of treatment will all be analysed in the same statistical model.

The interactions of site-by-treatment and baseline-by-treatment will be investigated separately in the model and will only be included in final model if they are statistically significant at the alpha=5% level. An unstructured (UN) covariance will be assumed. If the model does not converge using the unstructured covariance structure, the autoregressive (order 1) AR(1) structure will be used. If this also does not converge other covariance structures deemed appropriate to fit the data will be used.

For each visit, the adjusted means for each treatment and the estimated treatment differences for the treatment comparisons will be presented together with 95% confidence intervals for the differences and p-values for the treatment comparisons.

|  |                                    |                                  |
|--|------------------------------------|----------------------------------|
| Protocol Number:
GPL/CT/2014/018/III
(Study No. GSP 301-303) | SAP Version Number:
Version 1.0 | SAP Version Date:
04-Apr-2017 |
|--|------------------------------------|----------------------------------|

The adjusted means and estimated treatment differences for the treatment comparisons will also be plotted, with corresponding 95% confidence intervals.

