LSMeans, Std Err of LSMeans, 95% confidence intervals and p-values are based on separate mixed model repeated measures models for each week assessment, with change from baseline as dependent variable, treatment group and site as fixed effect, baseline as covariate, and week as the within-subject effect.

Programming note: the interaction terms treatment\*baseline and treatment\*site will only be included in the footnote if significant in the model

Data source: xx

Created on: ddmmyy hh:mm

Page 1 of N

|  |                                    |                                  |
|--|------------------------------------|----------------------------------|
| Protocol Number:
GPL/CT/2014/018/III
(Study No. GSP 301-303) | SAP Version Number:
Version 1.0 | SAP Version Date:
04-Apr-2017 |
|--|------------------------------------|----------------------------------|

**T14.1.9.12.3 Summary of Average AM rTNSS  
(Per Protocol Set)**  
Repeat of Table T14.1.9.12.1 for Per Protocol Set

**T14.1.9.12.4 Summary of Repeated Measures Analysis Results in Average AM rTNSS over the First 6, 30, and 52 Weeks of Treatment  
(Per Protocol Set)**  
Repeat of Table T14.1.9.12.2 for Per Protocol Set

**T14.1.9.12.5 Subgroup Analyses (Age Group): Summary of Average AM rTNSS  
(Full Analysis Set)**  
Repeat of Table T14.1.9.12.1 for age group

**T14.1.9.12.6 Subgroup Analyses (Sex): Summary of Average AM rTNSS  
(Full Analysis Set)**  
Repeat of Table T14.1.9.12.1 for sex

**T14.1.9.12.7 Subgroup Analyses (Race): Summary of Average AM rTNSS  
(Full Analysis Set)**  
Repeat of Table T14.1.9.12.1 for race

**T14.1.9.12.8 Subgroup Analyses (Ethnicity): Summary of Average AM rTNSS  
(Full Analysis Set)**  
Repeat of Table T14.1.9.12.1 for ethnicity

|  |                                    |                                  |
|--|------------------------------------|----------------------------------|
| Protocol Number:
GPL/CT/2014/018/III
(Study No. GSP 301-303) | SAP Version Number:
Version 1.0 | SAP Version Date:
04-Apr-2017 |
|--|------------------------------------|----------------------------------|

**T14.1.9.13.1 Summary of Average AM iTNSS  
(Full Analysis Set)**

| Treatment Group                          | Week     | Observed Data |             |        |            | Change from Baseline |             |        |            |
|--|----------|---------------|-------------|--------|------------|----------------------|-------------|--------|------------|

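### A 5% pre-test of two interactions decides which model gives the reported efficacy difference, so what is estimated can vary between analyses and, if site-by-treatment enters, the estimate can be lost

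*SAP*

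**What the plan says.** SAP 12.3.2.1 (rTNSS) and 12.3.2.2 (iTNSS) specify a repeated-measures model for the FAS and the PPS. The default is additive: "model change = treatment site baseline week". The treatment difference, its 95% CI and its p-value come from "lsmeans treatment / cl diff e". The two interactions are tested first, and the terms "will only be included in final model if they are statistically significant" at the 5% level. SAP 12.3.2.3 repeats the rule for overall RQLQ(S) in the FAS: "site-by-treatment and baseline-by-treatment will be investigated separately in the model".

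For rTNSS and iTNSS, "The responses for the first 6, 30 and 52 weeks of treatment will all be analysed in separate statistical models". For RQLQ(S), the three visits share one model with a week-by-treatment term.

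The SAS code is given only for the case where neither interaction is significant. For the other case there is no code, no LS-means weighting, no site-pooling rule and no fallback. The table shells have one set of rows per period. Their only trace of a changed model is a programming note that the interaction terms "will only be included in the footnote if significant in the model".

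On allocation, SAP 1.0 corrects protocol 10.3: "the randomization will not be stratified by site". Under protocol section 13 the SAP prevails. Protocol 13.5 adjusts for treatment, site and baseline only. SAP 1.0 records the move from ANCOVA to a repeated-measures model but does not mention the interaction rule.

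**The concern.** A rule that tests an interaction and then keeps or drops it lets the observed data decide what the headline number means. Under the additive model the difference is pooled across sites, and sites with more information count for more. With site-by-treatment in the model, the same LS-means statement gives every site equal weight, however small. With baseline-by-treatment in the model, the reported value is the effect at the mean baseline.

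The tests are run separately for each rTNSS and iTNSS horizon, so the 6-, 30- and 52-week rows of one table could carry different estimands. They are also run separately in the FAS and the PPS. SAP section 10.0 uses the PPS to check the robustness of the FAS result, and an apparent disagreement could arise only because a pre-test went the other way.

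The equally weighted average also needs a GSP 301 and a comparator-placebo subject at every site. If one site lacks either, SAS returns a non-estimable result and the main efficacy row for that horizon is blank.

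**Working it through.** The plan states no figure that depends on this rule, so there is none to reproduce. The arm size used below does follow from the stated attrition: 300/(1 − 0.25) = 400 and 100/(1 − 0.50) = 200, so 400 covers both exposure targets.

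**Inputs from the documents.** 600 subjects, 400/100/100 (SAP 8.0); 4:1:1 allocation, so the comparator placebo is 1 in 6 (SAP 7.0); no stratification by site (SAP 1.0); test level 5% (SAP 12.3.2.1).

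**Assumed.** The number of sites S; protocol section 9 says only that there are multiple US sites. Sites are taken as equal, n = 600/S.

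**Step 1: chance of an empty cell.** A site of n subjects has no comparator-placebo subject with probability (5/6)^n. For S sites, P(at least one) = 1 − (1 − (5/6)^n)^S. A site with no GSP 301 subject adds almost nothing: (1/3)^15 is below one in ten million.

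**Step 2: chance of losing the estimate.** This needs an empty cell and a significant site-by-treatment test. With no true interaction the second has probability 0.05, so the joint chance per model is about 0.05 × P(empty).

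| S | n | (5/6)^n | P(empty) | 0.05 × P(empty) |
|---|---|---|---|---|
| 10 | 60 | 0.00002 | 0.02% | about 0% |
| 20 | 30 | 0.0042 | 8.1% | 0.4% |
| 30 | 20 | 0.0261 | 54.7% | 2.7% |
| 40 | 15 | 0.0649 | 93.2% | 4.7% |

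**Step 3: check by simulation.** This used a single-outcome analogue of the model, residual SD 1, equal sites, central blocks of 6 and 2,000 runs per case. In the second column the site-specific treatment effects have SD 0.3, an assumed value.

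| S | Estimate lost, no true interaction | Estimate lost, site effects differ (SD 0.3) |
|---|---|---|
| 10 | 0% | 0% |
| 20 | 0.25% | 1.95% |
| 30 | 2.95% | 14.5% |
| 40 | 5.0% | 20.65% |

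**Step 4: effect of switching when the estimate exists.** Between the two models the estimate moved with an SD of 0.26 to 0.51 standard errors, and the standard error rose by 2% to 10%.

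**Step 5: how often the model changes.** With two tests per model and no true interaction, the chance that at least one term enters is 1 − 0.95² = 9.75% per model if the tests are independent.

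**Step 6: Type I error.** With zero average effect, the additive model rejected in 4.1% to 5.9% of runs and the test-then-include strategy in 3.7% to 5.9%. The Monte Carlo SE is √(0.05 × 0.95/2000) = 0.5 percentage points. Lost estimates were counted as non-rejections, so the clearest comparison is at 10 and 20 sites, where few or none were lost: 4.65% to 5.85% for the additive model against 4.55% to 5.9%.

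**The case against.** The strongest reply is that the procedure is laid down in advance. The base model, the two candidate terms, the threshold and the default code are all in the SAP. That is correct: a reader might infer that the analysis is not pre-specified, and the text does not support this. It is a pre-specified algorithm whose result depends on the data.

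Other stronger readings also fail:

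- **That an empty cell alone loses the estimate.** The site-by-treatment test must also be significant. Baseline-by-treatment never makes the difference non-estimable.
- **That lack of stratification is the cause.** It is one contributor. With uneven sites (assumed gamma sizes), empty cells occurred in 31%, 88% and 99.6% of simulated trials at 10, 20 and 30 sites under central allocation. Site-stratified blocks of 6 (also assumed) still gave 13%, 56% and 91%. Small sites and the 1-in-6 comparator matter too.
- **That some model will probably be altered by chance.** The FAS has 7 models and 14 tests, and 1 − 0.95^14 = 51%. But half of those tests concern baseline. Independence also fails, because the horizons are nested and both scores come from the same diary, so 51% is too high.
- **That RQLQ(S) visits can come from different models.** They share one.
- **That Type I error is inflated.** The simulation shows no clear sign of it.

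It is also fair that equal weighting and non-estimability follow only if the LS-means statement is reused once site-by-treatment is in the model. The SAP shows that statement only for the non-significant case, but it offers no alternative. Finally, efficacy is a secondary objective, SAP 6.0 states no hypotheses, and the primary safety analysis is untouched. These points limit the size of the problem; the stated rule remains.

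**Conclusion.** The point holds in limited form. For rTNSS, iTNSS and overall RQLQ(S), the stated 5% rule lets the data choose the reported treatment difference. For rTNSS and iTNSS that choice can differ between horizons and between FAS and PPS. Loss of the estimate is possible but not established as likely: with no true interaction it is roughly 0% to 5% per model over 10 to 40 equal sites, and higher if sites truly differ. These figures rest on an assumed site count, equal site sizes and reuse of the LS-means statement. The existence of the rule and the silence on the significant case rest on the SAP text alone. The change is worth making because it removes the ambiguity at almost no cost, not because a secondary result is known to be wrong.

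**What to change.** Before database lock and unblinding, amend SAP 12.3.2.1 to 12.3.2.3 as follows:

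- State that the final model for rTNSS and iTNSS is the additive one already coded, and for RQLQ(S) that model plus week-by-treatment, whatever the interaction p-values.
- Fit site-by-treatment and baseline-by-treatment each in a separate exploratory model, reported as a consistency check.
- Delete the sentence saying the terms "will only be included in final model if they are statistically significant".
- Delete the matching programming notes in the shells for these endpoints (T14.1.9.12.2, 13.2 and 14.2).
- Delete the same note in the shells for the other efficacy endpoints, such as T14.1.9.15.2, 17.1, 18.1 and 19.2. SAP 12.4.1 says interactions will not be investigated there, so those notes contradict it.

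The additive model does not need every arm at every site, so the remedy works without site stratification. The cost is SAP and shell wording; no data collection changes and the interaction results are still reported. The one trade-off is that, if sites truly differ, the headline figure remains a pooled effect and the variation appears only in the exploratory output.

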## 8.0 Sample Size Determination

The sample size of 600 subjects for this study (400 subjects on GSP 301 NS and 100 subjects in each of the 2 placebo groups) is based on the ICH E1 Guideline (ICH E1) and the FDA Guidance on Allergic Rhinitis which requires treatment of at least 300 subjects for 6 months and 100 subjects for 1 year. Based on an estimated attrition rate of 25% after 6 months and 50% after 52 weeks, 400 subjects in the GSP 301 NS treatment group are considered sufficient to meet the above requirements.

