### Derivation Method and Baseline

#### Mixed Model Repeated Measures (MMRM) Approach

Change from baseline in average AM rTNSS to the end of each treatment week will be derived as the average of post-baseline AM rTNSS scores by week (i.e average AM rTNSS score for Week 1 is calculated as the mean rTNSS score in Week 1), where baseline is defined as the average of the last 4 consecutive AM assessments during the last 4 days of the run-in period from the Day -3 AM assessment to the AM assessment on the day of randomization. At least 2 out of 4 assessments (scores) should be available in order to

|   |   |   |
|---|---|---|
|  | STATISTICAL ANALYSIS PLAN          |   |
| Protocol Number:
GPL/CT/2014/018/III
(Study No. GSP 301-303)         | SAP Version Number:
Version 1.0 | SAP Version Date:
04-Apr-2017 |

calculate the baseline scores for the AM rTNSS. In order to calculate the average of post-baseline AM rTNSS scores by week, at least 2 scores need to be present.

The same derivation method will also be applied to all other nasal symptom efficacy endpoints.

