### **12.3.2.2 Change from baseline in the average AM iTNSS over the first 6, 30 and 52 weeks of treatment**

AM iTNSS will be analyzed using same methods as described in Section [12.3.2.1](#).

The efficacy endpoints iTNSS will be analyzed using a mixed model repeated measures model, adjusting for covariates that include treatment, site, baseline and week as the within-subject effect (for both the FAS and the PPS). The interactions of site-by-treatment and baseline-by-treatment will be investigated separately in the model and will only be included in final model if they are statistically significant at the  $\alpha=5\%$  level. An unstructured (UN) covariance will be assumed. If the model does not converge using the unstructured covariance structure, the autoregressive (order 1) AR(1) structure will be used. If this also does not converge other covariance structures deemed appropriate to fit the data will be used. This method will assume that any missing data is Missing at Random (MAR). The statements of a

|  |                                    |                                  |
|--|------------------------------------|----------------------------------|
| Protocol Number:
GPL/CT/2014/018/III
(Study No. GSP 301-303) | SAP Version Number:
Version 1.0 | SAP Version Date:
04-Apr-2017 |
|--|------------------------------------|----------------------------------|

SAS PROC MIXED analysis would be (if the interactions of treatment\*baseline and treatment\*site is not statistically significant):

```
proc mixed;
class subject treatment site week;
model change = treatment site baseline week;
repeated week / subject = subject type=UN;
lsmeans treatment / cl diff e ;
ods output lsmeans=lsmeans ;
ods output diffs=diffs ;
run ; quit ;
```

The adjusted means for each treatment and the estimated treatment differences for the treatment comparisons will be presented together with 95% confidence intervals for the differences and p-values for the treatment comparisons. The adjusted means and estimated treatment differences for the treatment comparisons will also be plotted, with corresponding 95% confidence intervals.

The responses for the first 6, 30 and 52 weeks of treatment will all be analysed in separate statistical models.

A multiple, imputation-based approach may be considered for handling missing data for AM iTNSS upon review of amount of missing data observed.

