**12.4.2.2 Change in the average AM subject-reported rTNSS and iTNSS from baseline to the end of each treatment week**

The efficacy endpoints rTNSS and iTNSS will be analyzed separately using a mixed model repeated measures model, adjusting for covariates that include treatment, site, baseline and week as the within-subject effect, and the model will include treatment\*week interaction term (for the FAS). The statements of a SAS PROC MIXED analysis would be:

```
proc mixed;
```

|  |                                    |                                  |
|--|------------------------------------|----------------------------------|
| Protocol Number:
GPL/CT/2014/018/III
(Study No. GSP 301-303) | SAP Version Number:
Version 1.0 | SAP Version Date:
04-Apr-2017 |
|--|------------------------------------|----------------------------------|

```
class subject treatment site week;
model change = treatment site baseline week treatment*week;
repeated week / subject = subject type=UN;
lsmeans treatment treatment*week / cl diff e ;
ods output lsmeans=lsmeans ;
ods output diffs=diffs ;
run ; quit ;
```

For each week, the adjusted means for each treatment and the estimated treatment differences for the treatment comparisons will be presented together with 95% confidence intervals for the differences and p-values for the treatment comparisons. The adjusted means and estimated treatment differences for the treatment comparisons will also be plotted, with corresponding 95% confidence intervals.

Descriptive statistics (number of subjects, mean, standard deviation, median, minimum and maximum) will be provided for baseline, post treatment and change from baseline by treatment group and week (for both the FAS and the PPS).

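### If the unstructured fit fails, the 30- and 52-week symptom models must fall back on plain AR(1), whose standard errors are too small when subject-level correlation persists

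*SAP*

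**What the plan says.** SAP 11.1 makes the weekly mean the unit of analysis: the endpoint "will be derived as the average of post-baseline AM rTNSS scores by week". SAP 12.3.2.1 then fits a repeated-measures model with treatment, site, baseline and week. There is no treatment-by-week term, so the estimate is one difference pooled over the period. On the three periods it says "The responses for the first 6, 30 and 52 weeks of treatment will all be analysed in separate statistical models".

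The covariance rule has three steps:

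1. "An unstructured (UN) covariance will be assumed".
2. "If the model does not converge using the unstructured covariance structure, the autoregressive (order 1) AR(1) structure will be used".
3. "If this also does not converge other covariance structures deemed appropriate to fit the data will be used".

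SAP 12.3.2.2 (iTNSS) repeats the rule ("the autoregressive (order 1) AR(1) structure will be used"), and so does 12.4.2.1 (individual nasal symptoms). The printed code has a `REPEATED` statement only, with no `RANDOM` statement and no `EMPIRICAL` option. The week-by-week models in 12.4.2.2 and 12.4.2.3 also specify "repeated week / subject = subject type=UN" over 52 weeks but state no fallback. On dropout, SAP 8.0 says "Based on an estimated attrition rate of 25% after 6 months and 50% after 52 weeks".

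**The concern.** Steps 2 and 3 are both triggered by non-convergence, never by poor fit. AR(1) has two parameters and will almost always converge, so in practice it ends the sequence however badly it describes the data.

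The precision of a difference averaged over 30 or 52 weeks depends mainly on long-lag correlation. AR(1) takes its single correlation parameter largely from neighbouring weeks and forces geometric decay: 0.75 week to week implies 0.75^12 = 0.03 between Weeks 1 and 13. Eligibility requires at least two years of documented disease and expected allergen exposure throughout (Protocol 9.1), so lasting differences between subjects are plausible, and one baseline value removes only part of them. If they remain, AR(1) treats a long average as more precise than it is.

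At stake are the 95% confidence intervals and p-values for the 30- and 52-week rTNSS, iTNSS and individual-symptom results. Part of any narrowing of the interval from 6 to 52 weeks could also be an artefact, because the 6-week model, with few parameters, would probably stay unstructured.

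**Working it through.** **The plan's own figure.** 400 × (1 − 0.25) = 300 at 6 months and 400 × (1 − 0.50) = 200 at 52 weeks, against the required 300 and 100. SAP 8.0 reproduces. It gives no efficacy SD, power or within-subject correlation.

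**Size of the unstructured matrix,** T(T+1)/2:
- 6 weeks: 6 × 7/2 = 21
- 30 weeks: 30 × 31/2 = 465
- 52 weeks: 52 × 53/2 = 1,378
- RQLQ(S), three visits: 3 × 4/2 = 6

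**Inputs from the SAP.** 400 v 100 (12.3 compares with one placebo); attrition of 25% and 50%, taken as linear to Week 52; treatment, week and baseline terms; 95% intervals.

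**Assumed inputs.** With total variance 1, the correlation between weeks t and u (t ≠ u) is s + (1 − s − e)φ^|t−u|. Here s is the lasting subject share, φ the weekly decay and e independent weekly noise. Baseline is treated as one more value from the same structure and adjusted for with a common slope. Raw lag-1 correlation is s + (1 − s − e)φ.

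**Method.** Fit AR(1) by quasi-likelihood, then compare the model-based SE of the treatment coefficient with its true (sandwich) SE. True error of a nominal 5% test = 2[1 − Φ(1.96 × ratio)].

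| s, φ, e | raw lag-1 | SE ratio, 30 / 52 wk | true error, 30 / 52 wk |
|---|---|---|---|
| 0.5, 0.6, 0.10 | 0.74 | 0.62 / 0.51 | 23% / 32% |
| 0.5, 0.8, 0.10 | 0.82 | 0.69 / 0.59 | 17% / 25% |
| 0.3, 0.7, 0.10 | 0.72 | 0.72 / 0.61 | 16% / 23% |
| 0.2, 0.8, 0.10 | 0.76 | 0.80 / 0.71 | 12% / 16% |
| 0.4, 0.9, 0.05 | 0.90 | 0.84 / 0.76 | 10% / 14% |
| 0.2, 0.95, 0.02 | 0.94 | 0.98 / 0.94 | 6% / 7% |

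Worst row at 52 weeks, in SD units: AR(1) reports 0.0316 and the truth is 0.0619. The ratio is 0.51; 1.96 × 0.51 = 1.00; 2[1 − Φ(1.00)] = 32%. The baseline slope there is about 0.52, so the long-lag correlation left after adjustment is (0.5 − 2 × 0.52 × 0.5 + 0.52²)/(1 − 2 × 0.52 × 0.5 + 0.52²) = 0.25/0.75 = 0.33.

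**Controls.** With a true AR(1) at 0.75 the ratio is 1.03-1.05 after baseline adjustment and 1.00 without it, so there is no inflation. At 6 weeks the ratio over the six rows is 0.93-1.00.

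**Simulation,** 800 trials each, baseline in the model, AR(1) re-estimated every time (30 / 52 weeks):
- lag-1 0.74: 20.7% / 32.9%
- lag-1 0.76: 11.3% / 18.0%
- lag-1 0.87: 5.9% / 9.2%
- lag-1 0.94: 4.8% / 7.2%
- exact AR(1): 3.6% / 4.3%

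Sandwich standard errors in the same trials give 3.7-6.2%.

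**Other assumptions.** If such structures describe what remains after adjustment, a grid of 102 settings (lag-1 0.70-0.955) gives 5-29% at 30 weeks and 6-37% at 52. A separate calculation with a lasting correlation of 0.5, decay 0.6 and no weekly noise, baseline or site terms gives 0.0579/0.0870 = 0.67 (19%) at 30 weeks and 0.0491/0.0878 = 0.56 (27%) at 52. Simulation of that case gives 21.7% and 30.5%.

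**Interval narrowing,** with s = 0.2, φ = 0.8, e = 0.1 taken as the residual structure. The unstructured SE at 6 weeks is 0.0923; AR(1) at 52 weeks reports 0.0451 when the truth is 0.0677. Reported fall: 1 − 0.0451/0.0923 = 51%. Real fall: 1 − 0.0677/0.0923 = 27%. Artefact share: 0.0226/0.0472 = 48% (31-88% over six settings).

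**Proposed fallback.** Random intercept plus AR(1), model-based SE: ratio 1.00 in all six rows at 30 and 52 weeks, with and without the baseline term.

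**The case against.** The strongest reply is that two unproven conditions are needed.

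First, the unstructured fit must fail, and a parameter count does not show that it will. Under monotone dropout the estimate exists when the subjects still observed comfortably outnumber the weeks. Applying 50% attrition to all 600 leaves about 300 against 52 weekly values. One simulated dataset each at 500 and 600 subjects (241 and 321 completers) gave a valid 52-week matrix. That stands: 1,378 parameters make failure a realistic risk, not a certainty, and site effects and intermittent missing weeks add to it. The SAP itself plans for failure.

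Second, the residual correlation must outlast AR(1) decay. The documents do not say whether it does, and the error ranges from almost nothing to severe depending on that input. This also stands. It is a reason not to commit in advance to the one structure that cannot carry a lasting subject level.

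The consequence is limited too. The primary objective is safety, SAP 6.0 states no hypotheses, and the sample size does not rest on efficacy. The error rates above describe nominal p-values, not a confirmatory decision. Protocol 13 lets departures from the SAP be justified in the study report, but a structure chosen after unblinding is weaker than one named now. Finally, the printed code is for the unstructured fit, so the absence of robust errors in the fallback is inferred. Nothing in the text adds them.

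**Conclusion.** The point holds as a conditional one. If the unstructured fit does not converge, the SAP commits the 30- and 52-week rTNSS, iTNSS and individual-symptom models to plain AR(1) with model-based errors. If within-subject correlation then persists, intervals are too narrow and p-values too small: true error of about 6-23% at 30 weeks and 7-32% at 52 weeks against a nominal 5%, over the six structures tabulated. The direction rests on correlation decaying more slowly than AR(1) allows; the size rests wholly on assumed correlations. The calculations also assume linear dropout unrelated to outcome, two arms and no site terms.

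There is no effect if the unstructured fit converges, and no inflation if the residual correlation really is AR(1). The primary safety analysis is untouched. The weekly contrasts in 12.4.2.2 and 12.4.2.3 are not part of these figures. The change should be made before unblinding; confidence is medium because both conditions are unverified.

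**What to change.** In SAP 12.3.2.1, 12.3.2.2 and 12.4.2.1, replace the AR(1) fallback. If the unstructured model does not converge, fit a random subject intercept with an AR(1) residual:

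`random intercept / subject=subject;`
`repeated week / subject=subject type=AR(1);`

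Request sandwich standard errors (`proc mixed empirical`) whenever the structure is not unstructured. Keep the existing last step for the case where this also fails to converge. Name the same fallback in 12.4.2.2 and 12.4.2.3, which have none.

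RQLQ(S) in 12.3.2.3 (three visits, 6 parameters) needs no change. Section 12.4.2.4 borrows its method from 12.3.2.2, and 12.4.2.5 builds on it, so the new fallback would carry over to those three-visit models. That is harmless, but worth a sentence.

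The cost is two lines of SAS and one sentence per section, and usually wider intervals. The new structure contains plain AR(1) as a special case, so little is lost if AR(1) is right. Sandwich errors correct the standard error but not bias from a wrong covariance when dropout is missing at random, so the random intercept should come first and the sandwich should not stand alone.
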